SANTA CATARINA STATE UNIVERSITY - UDESC CENTER FOR HEALTH AND SPORTS SCIENCES – CEFID GRADUATE PROGRAM IN PHYSICAL THERAPY

[name]

EFFECT OF PREOPERATIVE PATIENT EDUCATION PROGRAM ON FUNCTIONAL OUTCOMES AFTER TOTAL KNEE ARTHROPLASTY

STUDY PROTOCOL

FLORIANÓPOLIS 2017

ABSTRACT

The knee is one of the joints most affected by osteoarthritis (OA), causing individuals to present joint stiffness, muscle weakness and proprioceptive deficit limiting the performance of daily activities. Total knee arthroplasty (TKA) presents good results in reducing the pain and stiffness of individuals in the final phase of OA. However, changes in gait and strength may persist postoperatively. Preoperative guidance for TKA were efficient in reducing pain and functional deficits and improving quality of life, however the functionality was measured by scales. Thus, this study aims to evaluate the effect of preoperative guidance on three-dimensional gait analysis, functional mobility, postural control and kinesiophobia level in subjects with TKA. Will be recruited patients of both sexes undergo unilaterally TKA in the city of Florianópolis and referred by an orthopedist to the Physiotherapy Clinic of UDESC. These will be divided into two groups: one that will receive verbal guidance and a leaflet with information related to their physical condition as well as signs and symptoms in the postoperative period and a group that will receive only verbal guidance. Both groups will be evaluated by a blind evaluator in the preoperative and postoperative periods (6 weeks and 6 months). The evaluations will be divided into five stages. Anthropometric measurements of the individual will be made and then the WOMAC functionality questionnaire and the Tampa Scale of Kinesiophobia will be applied. Then the individual will walk by 5 meters for three-dimensional gait analysis through the Vicon System, AMTI Force Platforms and Noraxon electromyograph. A functional mobility assessment will also be performed by Timed Up And Go. Finally, evaluation of the postural control with Neurocom Equilibrium Platform will be performed. Statistical data will be analyzed by analysis of variance 3x2 considering time factor (pre, post 6 weeks and post 6 months) and groups (with and without information leaflet). The p-value used will be 0.05.

Palavras-chave: osteoarthrosis, total knee arthroplasty, physiotherapy, gait analysis, guidance

1 INTRODUCTION

1.1 CONTEXTUALIZATION OF THE PROBLEM

The current extension of life expectancy leads to an increase in the elderly population, commonly affected by degenerative diseases such as osteoarthrosis (OA) (MILNER, 2009; YAARI et al, 2015). OA is the chronic-degenerative disease that most affects the elderly. In Brazil there is a lack of consistent data, but a prevalence of 26.5% is inferred. The knee is especially affected, between 23% and 40% of the elderly population, being more prevalent in women and over 74 years (SALVATO et al, 2015). Its onset and progression may be related to age, changes in metabolism, genetic and hormonal factors, biomechanical changes and inflammatory joint processes. The symptomatology goes from pain and joint stiffness to deformities and progressive loss of function (SANTOS et al, 2011). Thus, the treatment of this population should seek to reestablish independence and quality of life, where the resource commonly used in the final stages of OA is total knee arthroplasty (TKA) (HIYAMA et al, 2015).

The articular surface replacements began in the 1940s, undergoing continuous advances (VASCONCELOS et al, 2013), and are today the most effective surgery interventions in terminal phases of OA for success in reducing pain and joint stiffness (CASARTELLI et al, 2013). However, changes in strength, joint mobility, and gait may remain or worsen after joint (HIYAMA et al, 2015).

The recovery of gait function is one of the main objectives after TKA (CASARTELLI et al, 2013), because this activity is related to the independence of the individual besides being one of the activities that presents a higher incidence of fall in the elderly (HALLAL et al, 2013). Abnormal gait patterns may predispose to new degenerative processes or early deterioration of the prosthesis. Thus, identifying abnormalities makes it possible to trace treatment strategies for its correction (MILNER, 2009).

The use of scales and questionnaires is highly used in the evaluation of pain and post-TKA functionality. However, the subjectivity of these evaluations interferes in the quantification of the functional framework and, therefore, in the therapeutic direction. Evidence suggests that measures based on performance are more likely to characterize changes in function than self-reports (YUKSEL et al, 2016).

Investigations of the kinematics in the TKA showed lower flexion in the initial contact phase and less flexion in the oscillation phase. These individuals also had greater varus in response to the load when compared in asymptomatic individuals (VASCONCELOS et al, 2013). Research associating three-dimensional gait assessment with electromyography (EMG) found patterns that differed from normal, but no preoperative data were collected from individuals in order to quantify the changes that occurred (VILLARDI et al, 2005; LEE et al, 2015).

He knows that the variability of step time depends on the sum of factors physical function, ability to balance and mental state, such as the confidence of the individual in his ability to perform the activity (HYIAMA et al, 2015). There is evidence that persistence of pain can not be based solely on clinical findings, making a purely clinical intervention inefficient (SIQUEIRA et al, 2007). Pain education can alter beliefs about pain, such as the fact that it is related to tissue damage and disability (LOUW et al, 2013), Showing reduction of pain, functional deficits and improvement of the quality of life in patients who received guidance for the postoperative period (MONTICONE et al, 2013).

A review study has shown that preoperative guidance themselves can not modify the patient's physical condition but improve the ability to cope with pain and feel prepared for surgery by reducing anxiety and increasing postoperative comfort (AYDIN et al, 2015). Fear of movement pain characterizes kinesiophobia, where the individual ceases to perform activities inducing a vicious cycle, which results in decreased joint mobility, muscular strength and proprioception, thus increasing the pain experience (MONTICONE et al, 2013).

Although there were studies on the effect of preoperative guidance on patients with TKA, mobility was assessed only through functional questionnaires, with no objective information on the behavior of the spatial-temporal and kinetic parameters of gait, postural control and functionality. Thus, this study aims to evaluate the effect of preoperative guidances on functional gait recovery and kinesiophobia level in subjects post TKA.

1.2 OBJECTIVE

The study was designed to evaluate the effect of preoperative patient education program on functional outcomes after total knee arthroplasty.

1.3 HYPOTHESES OF RESEARCH

- H0: There is no difference on functional outcomes on functional otucomes after TKA in patients that received preoperative information and those who did not.
- H1: There is difference on functional outcomes on functional otucomes after TKA in patients that received preoperative information and those who did not

3 METHODOLOGY

3.1 STUDY DESIGN

This study is a single-center, prospective, parallel-group, randomized clinical trial (HULLEY et al, 2015).

3.2 PARTICIPANTS

Sample size estimation calculations were performed taking into consideration the primary outcome measure - Timed up and Go (TUG) test score. These calculations were based on the study published by Mizner et al (2005), and considering a Minimal Clinically Important Change of 2,27 seconds in the TUG score (Yuksel et al, 2016). Considering a power of 80% and a two-sided 0.05 significance level, 28 patients would be necessary to detect a 2.27 second difference between the two arms (14 patients in each arm). Considering a dropout rate of 10%, the total sample size would be 31 patients. We have decided to extend the sample size to 40 patients (20 patients in each arm), assuming small variations on the baseline TUG scores and standard deviation in the study population..

The sample will be recruited between patients of both sexes with indication for total unilateral knee arthroplasty in the city of Florianópolis and referred by orthopedic physicians. The collection will take place in the period between July 2017 and April 2018. Participants will be divided into two groups of equal size: intervention group (GI) who will receive preoperative oral guidance and a leaflet with information related to their physical condition as well as signs and symptoms in the postoperative period (APPENDIX A); Control group (GC) who will receive only verbal guidance in the preoperative period.

The evaluations will occur in three moments (preoperative, 6 weeks and 6 months after the arthroplasty). On the day of the first collection, the participants will be allocated to each group according to the draw made by a team member who will not participate in the evaluations. This same member will deliver the package leaflet to the GI participants. Evaluators will be blinded to individuals participating in IG and GC. All participants will receive information about the objectives and procedures of the study through the Informed Consent Form (APPENDIX B) prior to the collection.

3.2.1 Inclusion and exclusion criteria

The following criteria will be used:

Inclusion:

- Age above 55 years;

- Literate;

Elective submission of total unilateral knee arthroplasty (TKA) due to osteoarthrosis;
Que não tenham realizado substituição unicompartimental anterior ou osteotomia de tíbia no mesmo joelho;

- Who have not had knee infection or other serious complications after TKA;

- Body mass index less than 40 kg / m2;

- That he has not performed other arthroplasties on the lower limb in the last 6 months;

- Movement arc greater than 90° in the operated or contralateral knee.

Exclusion

- Associated condition that impedes performance in gait tests, including significant osteoarthrosis in the contralateral knee or hips (defined as pain greater than or equal to 5 in VAS);

- Absence or abandonment in the study follow-up sessions.

Blinding

The nature of the study will allow blinding of the patients regarding study arms. Participants will be blinded to the primary and secondary outcomes being measured. Baseline patient assessment, as well as outcomes assessment at 6 weeks and 6 months will be performed by one investigator blinded for experimental or active comparator arms. Statistical analysis will be performed blinded for experimental or active comparator arms. Patient assessment

Patients will be assessed at baseline (pre-operatively), in 6 weeks after surgery and 6 months fter surgery.

Baseline assessment

Participant characterization will consist of:

- a) Demographics (gender, date of birth);
- b) Educational level (years);
- c) Diagnosis
- d) Affected side
- e) Date of surgery
- f) Gait analysis
- g) Timed Up and Go test
- h) Knee Osteoarthritis Score WOMAC
- i) EMG muscle activity
- j) Kinesiophobia
- 1) Postural control

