3.5.5 Stage 5 – postural control

[figure not shown]
The NeuroCom SMART EquiTest CRS balancing platform will be used, with a sampling rate of 100 Hz. The equipment will be calibrated according to the manufacturer's standards. The collections will be made with three dynamic protocols pre-established by the system: Sensory Organization Test (SOT), which verifies the sensory motor control; Motor Control Test (MCT), which verifies the automatic motor control; And Adaptation Test (ADT), which verifies adaptive motor control.

All protocols will be performed in the bipodal position, where the individual will position their feet together, parallel, hands along the body and face facing forward. The tests performed will evaluate the posture control of the participant in static posture with open and closed eyes, without and with movement of the support surface and / or visual environment. The order of the three protocols (SOT, MCT and ADP) will be chosen by lot.

During collection the individual should stand at the base of the platform looking forward. He will wear harness (available in small, medium and large size) connected to safety cables throughout the test. During the test only the presence of the evaluator and one other member of the collection team will be allowed to assist the assessor in case of loss of balance. Both should be close to the individual, but should not interfere with the test.

You will be prompted to look at the screen in front of you and center the puppet (corresponding to the alignment of the participant). Before starting the tests the individual will be informed that the platform and the environment can move during the evaluation, but will not be informed about when this will occur. Afterwards, the researcher will start collecting the data, guiding the participant to keep the doll as centralized as possible without flexing the knees or changing the position of the feet. In cases where the participant uses these or other artifacts to maintain postural control (eg, hold in the environment), the test will be considered a "failure" and the test will continue for the next test.

Figura 1 – Data collection procedure diagram

The data collected in the preoperative period will be used as a comparative baseline to determine changes in gait parameters (spatio-temporal, kinetic, electromyographic), postural control and functionality associated with the presence or absence of information in the preoperative.

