APPENDIX C - Personal data and follow-up of participants

MASTER IN PHYSIOTHERAPY Preoperative guidance and repercussion in gait after

knee arthroplasty

Name:		Sex: ()F () M
Date of birth / age:		Telefone: ()
Address:		
Date of surgery:	Weight:	Height:
Antonion annonica in the	n anotad an aantralataral lan	

Anterior surgeries in the operated or contralateral knee:

Physiotherapeutic Treatment

PREOPERATIVE - Allocation () GI () GC

Do you do physiotherapy for your knee pain? If yes, how many times in the week?

What treatment time (weeks, months, years)?

Check the type of procedures you perform in the sessions:

() warmth () cold () TENS () US () stretches () strengthening exercises () balancing exercises () Others, which ones?

6 WEEKS AFTER SURGERY - Booklet reading () Yes () No () GC

Are you doing physiotherapy? If yes, how many times in the week? How long after the surgery did you start the sessions? If completed, how many sessions and for how long? Check the type of procedures you perform in the sessions: () warmth () cold () TENS () US () stretches () strengthening exercises () balancing exercises () Others, which ones?

6 MONTHS AFTER SURGERY - Booklet reading () Yes () No ()GC

\mathbf{U}
Are you doing physiotherapy? If yes, how many times in the week?
How long after the surgery did you start the sessions?
If completed, how many sessions and for how long?
Check the type of procedures you perform in the sessions:
() warmth () cold () TENS () US () stretches () strengthening exercises () balancing
exercises () Others, which ones?

ATTACHMENTS

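### Missed follow-up is an exclusion criterion, so as written the trial removes randomised patients for events after the draw, which can bias the TUG comparison

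*Protocol*

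**What the plan says.** Protocol section 3.2 places randomisation before surgery: "On the day of the first collection, the participants will be allocated to each group according to the draw". Follow-up visits come 6 weeks and 6 months after the operation. Section 3.2.1 then lists under Exclusion: "Absence or abandonment in the study follow-up sessions". Under Inclusion, among items of history, it has: "Who have not had knee infection or other serious complications after TKA".

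The sample-size text in section 3.2 expects some loss: "Considering a dropout rate of 10%, the total sample size would be 31 patients". The total is then raised to 40, 20 per arm. For TUG, the primary outcome, the SAP gives a 3x2 analysis of variance (three times, two groups), a sphericity correction and an effect-size measure. Neither document names an analysis set, mentions intention to treat, or says how a missing TUG value is handled.

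**The concern.** An exclusion criterion should be decidable before the draw. Attendance at follow-up can be known only afterwards, so this one cannot act as an eligibility screen. It can only take out patients who have already been allocated, and the protection that randomisation gives the comparison no longer covers those who remain.

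The planned analysis pushes the same way. A standard repeated-measures ANOVA needs all three visits, so someone seen at 6 weeks but not at 6 months contributes nothing. That is the avoidable part of the problem: TUG values that were measured and then thrown away. A patient with no postoperative visit supplies no postoperative TUG under any wording.

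The complication item is a separate, lesser matter, because its wording is ambiguous. It may refer to an earlier TKA. Section 3.2.1 limits other arthroplasties only by "That he has not performed other arthroplasties on the lower limb in the last 6 months", and Appendix C records "Anterior surgeries in the operated or contralateral knee". If it means the trial's own operation, it is a second removal after the draw.

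**Working it through.** **Order of events.** Draw at the preoperative visit (section 3.2); surgery; visits at 6 weeks and 6 months; exclusion for missing those visits (section 3.2.1). No statement in the SAP overrides the exclusion.

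**The plan's own figures.** 28 × 1.10 = 30.8, rounded up to 31, which reproduces the stated total. (28 / 0.90 = 31.1 would round up to 32.) With 40 randomised, a 10% loss is 4 patients, leaving 36.

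**Implied SD.** The documents give no SD for TUG. Solving back from 14 per arm, 2.27 s, 80% power and two-sided 0.05:
- Normal formula: 2.27 / ((1.960 + 0.842) × √(2/14)) = 2.14 s.
- Exact t test: 2.06 s.

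**Illustrative set-up (assumptions).** 20 per arm, no true effect, equal correlation ρ between visits of 0.3 to 0.7. Those lost attend week 6, miss month 6, and are the extremes of their arm at week 6. Removing the slowest 1, 2, 3 or 4 of 20 lowers that arm's week-6 mean by 0.098, 0.181, 0.259 or 0.332 SD (400,000 runs). Baseline falls by ρ times as much, so:

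bias in change from baseline to 6 weeks = shift × SD × (1 − ρ)

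For example, 4/0 at ρ = 0.3 gives 0.332 × 2.06 × 0.7 = 0.48 s and 0.332 × 2.14 × 0.7 = 0.50 s. Change from baseline is a relevant quantity here, because section 3.5.5 makes the preoperative data the comparative baseline.

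| Lost after week 6 | Shift (SD) | Bias in 6-week change, s (ρ = 0.3; 0.5; 0.7) | Time-by-group false positives at 5% (ρ = 0.3; 0.5; 0.7) |
|---|---|---|---|
| Nobody | 0 | 0 | 5.0; 5.1; 5.1% |
| Slowest 4 of 40, whichever arm | 0 on average | 0.00 | 4.9; 5.0; 4.9% |
| 2/2, slowest in both arms | 0 | 0 | 5.7; 5.5; 5.2% |
| 2/0, slowest | 0.181 | 0.26–0.27; 0.19; 0.11–0.12 | 6.4; 6.0; 5.5% |
| 3/1, slowest | 0.259 − 0.098 = 0.161 | 0.23–0.24; 0.17; 0.10 | 6.6; 6.1; 5.7% |
| 4/0, slowest | 0.332 | 0.48–0.50; 0.34–0.36; 0.21 | 8.9; 7.7; 6.7% |
| 2/2, slowest in one arm, fastest in the other | 2 × 0.181 = 0.362 | 0.52–0.54; 0.37–0.39; 0.22–0.23 | 10.3; 8.6; 7.2% |

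False-positive rates come from 100,000 simulated trials per cell, except the row for the slowest 4 of 40 (20,000 trials, SD 2.1 s). The 6-month change has about zero bias in this set-up, because baseline and month 6 shift equally and cancel.

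**A different loss model.** Suppose the chance of loss rises with TUG on a logistic scale, and the arms are compared by t test at one visit (SD 2.06 s, 10% loss). If loss depends on TUG in one arm only, the bias is 0.18 to 0.30 s, with 5.5% to 7.4% false positives. If it runs in opposite directions in the two arms, the bias is about 0.38 s, with about 8%. If it is unrelated to TUG, or related equally in both arms, the bias is about 0, with about 5%.

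**Power.** At SD 2.06 s, power is about 92% with 20 per arm and 89% with 18. The harm is mainly bias, not lost power.

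**Does using all visits help?** In the 2/0, 3/1 and 4/0 cases a likelihood estimate from all available visits had bias within 0.02 s at both follow-up visits (15,000 runs per cell). It also removed the bias in the opposite 2/2 case.

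**The case against.** The case for giving this little weight has several parts.

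- **Blinding makes differential loss less likely.** Section 3.2.1 says patients, the assessor and the analysis are blinded to arm, and both arms receive verbal guidance. This stands as mitigation. It does not rule the problem out, since the leaflet itself could affect who returns.
- **The unequal splits are chosen to be adverse.** This is fair. If loss is unrelated to arm, all four losses fall in one arm with probability 2 × C(20,4) / C(40,4) = 9,690 / 91,390 = 10.6%. Removing the slowest 4 of 40 whatever their arm gives no bias when there is no true effect.
- **The harm is narrow.** Only patients seen at one of the two follow-up visits have data that can be saved, and the criterion may simply be a loose description of dropout. Even on that reading, the ANOVA discards their data and no analysis set is stated.
- **The remedy can do worse.** In the cases above, loss depends on the observed week-6 value, so data are missing at random by construction. When the two slowest at month 6 in one arm miss that visit, simulations gave a 6-month bias of 0.17 to 0.33 s with available visits against 0.11 to 0.26 s with complete cases. This stands, and it is why a sensitivity analysis is needed.
- **The SD is uncertain.** Values from 1.98 to 2.14 s all return 14 per arm, and 1.98 in place of 2.06 lowers the biases by about 4%. If the implied SD is that of change, the 4/0 bias is 0.332 × SD × √((1 − ρ)/2), or 0.26 to 0.42 s, which lies inside the range shown.

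These points limit the size of the problem. None removes the rule from the protocol.

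**Conclusion.** The concern holds. The protocol states a rule that, applied as written, removes randomised patients for events after the draw, and the planned ANOVA in its standard form also discards partial data. The TUG comparison can be biased as a result. Expected bias is zero only if removal is unrelated to TUG, or if the same number and kind of patient leaves each arm; equal counts alone are not enough.

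Size and direction cannot be derived from the documents. In the illustrations, two one-sided losses move the 6-week change by 5% to 12% of the 2.27 s target (0.11 / 2.27 to 0.27 / 2.27), and four move it by 9% to 22%. These are not bounds. They rest on the back-solved SD, the assumed correlations, and the assumption that those lost are the extremes who attended week 6. With fewer such patients, or a looser link to TUG, the avoidable bias shrinks towards zero. The complication item counts only as wording to be reconciled.

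**What to change.** - Delete follow-up attendance from the exclusion list, and state that all randomised patients are analysed in the arm drawn.
- Reconcile the complication item so that eligibility rests only on history known before the draw. State that a patient with a postoperative complication stays in the analysis set; whether that patient undergoes testing remains a clinical decision.
- Analyse TUG with a method that uses every available visit, such as a linear mixed model for repeated measures, and state that it assumes data are missing at random.
- Add one sensitivity analysis that departs from that assumption, for example shifting imputed postoperative TUG in one arm at a time by amounts fixed in advance.
- Report attrition and complications by arm.

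The cost is protocol and SAP wording, a little more analysis and a count of complications by arm, with no extra patients or visits. Variance may rise slightly: in the illustration the sampling SD of the 6-month difference was 0.65 to 0.72 s with available visits against 0.65 to 0.71 s with complete cases. The model leans on an assumption that the data cannot confirm, and patients with no postoperative visit remain missing.
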